5.7 Subject Compliance Monitoring

Subjects will be required to maintain a pill diary documenting adherence to twice daily oral administration of abemaciclib. Study medication bottles will be brought to study visits at the start of each 28-day cycle and study diaries will be reviewed at the start of each cycle.

6 Study Procedures

Table 6: Schedule of Study Procedures

All labs and study visits have a window of +/- 4 days. All imaging has a window of +/- 7 days

Study Phase	Screening	Cycle 1 (35 days)				Cycle 2+ (28 days)		End of Study Visit ²	Follow-up ³
Study Days	-28 to 0	1 8 15¹ 29¹				1 15¹			
Treatment									
Abemaciclib		X-----				X			
Nivolumab			X			X			
Tests and Procedures									
Informed Consent	X								
Review Inclusion/ Exclusion Criteria	X								
Demographics/Medical History	X								X ³
Physical Examination	X	X	X			X		X	
Vital Signs: BP, HR, RR	X	X	X			X		X	
Height	X								
Weight	X	X				X		X	
ECOG PS	X	X	X			X		X	
Concomitant Medications	X	X				X		X	
IP Compliance						X		X	
AE Assessment		X	X			X		X	
CBC with differential ⁴	X	X	X	X	X	X	X ⁴	X	
Serum Chemistries ⁵	X	X	X	X	X	X	X ⁵	X	
TSH	X					X		X	
PT/aPTT ⁶	X					X ⁶		X ⁶	
Serum Pregnancy Test ⁷	X	X				X		X	
AFP ⁸	X	X ⁸				X ⁸		X ⁸	
HIV Screening ⁹	X								
Hepatitis B/C Screening ¹⁰	X	X ¹⁰				X ¹⁰		X ¹⁰	
Disease Assessment (CT or MRI) ¹¹	X					X		X	
Research Correlates									
Blood sample (50cc) ¹²	X		X	X ¹²		X		X	

CONFIDENTIAL

This material is the property of the University of Pennsylvania.

Tumor biopsy ¹³	X		X					
----------------------------	---	--	---	--	--	--	--	--

¹ Lab visit only

² Should occur within 30 days of end of protocol therapy

³ Follow-up will be through review of the available medical record and/or phone calls every 6 months for up to 2 years

⁴ CBC with differential including hemoglobin, white blood count, absolute neutrophil count, and platelet count. CBC will be repeated on day 15 of cycle 2 but is required on day 15 of subsequent cycles only if hematologic toxicity \geq Grade 2 by CTCAE v 5.0

⁵ Serum chemistries including sodium (Na), potassium (K), chloride (Cl), bicarbonate (HCO3), blood urea nitrogen (BUN), creatinine (Cr), albumin, total bilirubin, AST, ALT, and alkaline phosphatase. Chemistries will be repeated on day 15 of cycle 2 but are required on day 15 of subsequent cycles only if hepatotoxicity \geq Grade 1 by CTCAE v 5.0 or other toxicity measured by the panel \geq Grade 2 by CTCAE v 5.0 are present on day 1 of that cycle.

⁶PT/INR will be done at screening, day 1 of cycle 2 and subsequent cycles, and at the end of study visit. Activated thromboplastin time (aPTT) is required only at screening

⁷Women of childbearing potential per Appendix A

⁸AFP will be repeated only if abnormal at screening

⁹HIV screening with HIV1/2 antibody screening and HIV RNA PCR if antibody screen positive

¹⁰Hepatitis B screening with hepatitis B surface antigen, surface antibody, and core antibody (IgG or total antibody, not IgM); if hepatitis B surface antigen or core antibody is positive, HBV DNA PCR will be performed. Hepatitis C screening with HCV antibody; if positive, HCV RNA PCR will be performed. Subjects who are positive for HBV core antibody and/or surface antigen at screening must have HBV viral load checked on day 1 of each cycle and at the end of treatment visit.

¹¹Baseline imaging assessment to be performed within 21 days of cycle 1 day 1. Subsequent imaging on cycle 3 day 1 and on day 1 of every other subsequent cycle (cycles 5, 7, etc.), and at end of study visit if not performed within prior 28 days.

¹² Baseline research blood samples can be drawn during screen or prior to treatment on cycle 1 day 1, then on cycle 1 day 8 prior to nivolumab treatment, cycle 1 day 15-19 (on same day as research tumor biopsy when possible), day 1 of each subsequent cycle, and at the end of study visit. Procedures for sample handling are described in the laboratory manual.

¹³Core or surgical tumor biopsy must occur at baseline after completion of most recent therapy and between days 15 and 19 of cycle 1. Biopsies outside of this window for scheduling, safety, or other reasons will not be considered deviations but should be discussed with the Principal Investigator.

CONFIDENTIAL

This material is the property of the University of Pennsylvania.

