	Requirement for 10mg per day or greater of prednisone or equivalent for more than 12 weeks	Permanently discontinue
	Persistent grade 2 or 3 adverse reactions lasting 12 weeks or longer	Permanently discontinue

These dose adjustments are for AEs deemed related to nivolumab using CTCAE v. 5.0. If in the opinion of the treating Investigator, a toxicity is thought to be unrelated to nivolumab, no dose delay for nivolumab is necessary. If treatment is withheld per the above table, it should be held until the toxicity has returned to Grade ≤ 1 .

Subjects with drug-related endocrinopathies controlled with hormone replacement such as insulin or adrenal replacement-dose steroids may resume treatment when toxicity has improved to Grade ≤ 1 . Dose interruption is not required for hyper- or hypothyroidism but supportive care (e.g. thyroid replacement) should be started per institutional standards.

Corticosteroids are frequently indicated for Grade 3 or greater toxicities, and are necessary at times for lower grade toxicities. Guidance for their use and dosing is available in nivolumab package label. For any toxicity of nivolumab (regardless of grade) that, despite optimal supportive care, is felt by the treating Investigator to present a risk to safety of the study subject, additional treatment delay or treatment discontinuation is permitted at the discretion of the treating Investigator.

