6.2.3 Cycle 3 and beyond

6.2.3.1 Day 1

- Focused physical exam
- Vital signs and weight
- ECOG PS
- CBC with differential and platelet count and serum chemistries (Na, K, Cl, HCO₃, BUN, Cr, Ca, Alb, TBili, AST, ALT, ALP)
- TSH

CONFIDENTIAL

- PT/INR
- AFP (only if elevated at screening)
- Serum pregnancy test for beta HCG (for women of childbearing potential, defined in Appendix A)
- HBV DNA PCR if hepatitis B surface antigen or core antibody previously positive
- Review of concomitant medications
- Review of abemaciclib pill diary
- Dispensing of abemaciclib and return of unused pills
- AE assessment
- Nivolumab treatment
- Blood draw (50cc) for correlative research studies (procedures described in laboratory manual)
- Disease assessment (CT or MRI) with 7 days of day 1 of cycle 3, 5, and every other subsequent cycle

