7.10 Disease Assessments

7.10.1 Antitumor Effect

For the purpose of this study, patients will be evaluated for response every 8 weeks by CT scan of the chest with or without contrast and triphasic (non-contrast, arterial phase contrast, venous phase contrast) CT scan and/or MRI of the abdomen with IV contrast (pelvis required only if disease documented in pelvis on baseline scan). MRI scans of the abdomen are preferred if the patient is eligible to have this done. The same imaging modality should be used throughout the study.

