7.10.2 Definition of Evaluable

Evaluable for toxicity: All patients will be evaluable for toxicity from the time of their first treatment with abemaciclib.

Evaluable for efficacy endpoints, including overall response: Only those patients who have measurable disease present at baseline, have received at least one cycle of therapy (including at least 50% of scheduled abemaciclib doses and at least 1 dose of nivolumab), and have had their disease re-evaluated by appropriate imaging after at least 4 and no more than 12 weeks from cycle 1 day 1 will be considered evaluable for efficacy endpoints including overall response. These patients will have their response classified according to the definitions stated below.

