7.10.5.3 Immune-Related Response in Measurable Lesions (iRECIST)

iRECIST guidelines were established in 2017 to guide response assessments in clinical trials testing immunotherapeutics. Full details of the iRECIST criteria for this study can be found in Seymour L et al, Lancet Oncology 2017 [15].

If initial RECIST 1.1-defined progression (ie, iUPD) is noted on imaging in the setting of clinical stability, subjects may remain on study treatment and have confirmatory imaging in 4-8 weeks (study specified scans every 8 weeks should continue on initial schedule if patient remains on study). An assignment of clinical stability requires that no worsening of performance status has occurred, that no clinically relevant increases in disease-related symptoms such as pain or dyspnea occur that are thought to be associated with disease progression, and that no requirement for intensified management of disease-related symptoms exists, including increased analgesia, radiotherapy, or other palliative care. The imaging findings and the recommendation to continue with treatment despite iUPD should be discussed with the patient before a decision is made about whether or not to continue therapy. Patients who have iUPD and are not clinically stable should be designated as not clinically stable in the case report form. This designation will allow the

CONFIDENTIAL

This material is the property of the University of Pennsylvania.

best overall response to be calculated and the date of iUPD to be used in estimates of progression-free survival.

If radiologic progression is confirmed (iCPD), they will be determined to have progressive disease and discontinued from study therapy, but if repeat imaging shows stable disease or response by RECIST 1.1 they may remain on study therapy with imaging continuing as previously scheduled every 8 weeks (cycle 3 day 1, cycle 5 day 1, etc.).

Table 3: Comparison of RECIST 1.1 and iRECIST

	RECIST 1.1	iRECIST
Definitions of measurable and non-measurable disease; numbers and site of target disease	Measurable lesions are ≥ 10 mm in diameter (≥ 15 mm for nodal lesions); maximum of five lesions (two per organ); all other disease is considered non-target (must be ≥ 10 mm in short axis for nodal disease)	No change from RECIST 1.1; however, new lesions are assessed as per RECIST 1.1 but are recorded separately on the case report form (but not included in the sum of lesions for target lesions identified at baseline)

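### Scans are set by cycle number in the schedule but by 8-week intervals in section 7.10, and nothing says which governs if a nivolumab hold delays a cycle

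*Combined protocol and SAP*

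**What the plan says.** Two rules set the date of a scan.

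- **By cycle.** Table 6, footnote 11: "Subsequent imaging on cycle 3 day 1 and on day 1 of every other subsequent cycle". The visit list in section 6.2.3 agrees: "Disease assessment (CT or MRI) with 7 days of day 1 of cycle 3, 5, and every other subsequent cycle".
- **By calendar.** Section 7.10.1: "patients will be evaluated for response every 8 weeks by CT scan of the chest". It names no start date for the 8 weeks.

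Section 7.10.5.3 equates them: "imaging continuing as previously scheduled every 8 weeks (cycle 3 day 1, cycle 5 day 1, etc".

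Section 3.2 lists toxicities for which nivolumab is withheld, in a table whose title mentions delays. It then says: "If treatment is withheld per the above table, it should be held until the toxicity has returned to Grade" 1 or lower. Day 1 of cycle 2 and of each later cycle is the nivolumab day.

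Two sentences protect scan timing, and neither covers a temporary toxicity hold. Section 7.10.5.3, on unconfirmed progression, says "study specified scans every 8 weeks should continue on initial schedule if patient remains on study". Section 6.2.6 asks for scanning to continue where possible, but only after all study treatment has been permanently stopped.

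Evaluability depends on when the first follow-up scan is done. Section 7.10.2 requires it "after at least 4 and no more than 12 weeks from cycle 1 day 1". Section 8.4.2 also uses 4 to 12 weeks but counts from baseline imaging, which may be up to 21 days before cycle 1 day 1. Section 8.4.2 applies to PFS, ORR, DOR and OS, and it replaces subjects who do not qualify.

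**The concern.** Scan dates should not depend on how treatment is going. When a scan is tied to a treatment day, a subject whose treatment is delayed by toxicity is also imaged later. Two things follow.

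1. Progression found by scan is dated when it is documented (section 7.10.5.5 for DOR; section 7.10.7 runs PFS from start of treatment to progression). A later scan gives a later date, and this happens selectively in subjects with toxicity.
2. A late first scan can fall outside the 12-week limit. The subject has been treated and scanned, but leaves the efficacy analyses and is replaced. Subjects with early toxicity would then be removed selectively from the primary endpoint as well as from PFS, DOR and OS.

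**Working it through.** **Inputs.** Cycle 1 is 35 days, later cycles are 28 days, and the imaging window is +/- 7 days (all Table 6). Baseline imaging is 0 to 21 days before cycle 1 day 1 (footnote 11). The limit is 12 weeks = 84 days (sections 7.10.2 and 8.4.2).

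**The plan's own equivalence.** Section 7.10.5.3 puts cycle 3 day 1 at 8 weeks. From cycle 1 day 1 it is 35 + 28 = 63 days = 9 weeks, with a window of 56 to 70 days. Cycle 5 day 1 is 63 + 56 = 119 days = week 17. Counted from cycle 1 day 1, the two rules differ by one week at the first scan with no delay at all.

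**Effect of a delay.** Let D be the total delay in days before cycle 3 day 1. Under Table 6 the first scan moves to day 63 + D, and a progression already present on day 63 can be dated up to D days late. PFS starts at a fixed date, so it can only lengthen. DOR has two moving ends: a delay before response is recorded dates the response later and shortens DOR, while a delay before progression is recorded lengthens it. The net sign cannot be fixed.

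**Limit under section 7.10.2 (from cycle 1 day 1).**
- Nominal date: 84 - 63 = 21, so the limit is missed when D exceeds 21.
- Early edge of the window: 84 - 56 = 28, so it is missed when D exceeds 28.

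**Limit under section 8.4.2 (from baseline imaging).** With the baseline scan b days before cycle 1 day 1, the largest D that still meets the limit on the nominal date is 84 - 63 - b. Add 7 at the early edge and subtract 7 at the late edge.

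| b (days) | Nominal | Early edge | Late edge |
|---|---|---|---|
| 0 | 21 | 28 | 14 |
| 7 | 14 | 21 | 7 |
| 14 | 7 | 14 | 0 |
| 21 | 0 | 7 | -7 |

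With b = 21 the nominal scan falls exactly on day 84, so 1 day of delay misses the limit. More than 7 days misses it anywhere in the window. At the late edge the scan is on day 63 + 7 + 21 = 91, past the limit with no hold at all.

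**Primary test.** Section 8.3 states 81% power for 27 subjects. The exact rule is success at 8 or more responders of 27: type I error 0.0977 under 18%, power 0.812 under 36%. The figure is reproduced. Because excluded subjects are replaced, the number analysed and the nominal power do not change; what changes is who is counted.

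**The case against.** The strongest reply is that the premise is inferred. Section 3.2 speaks of withholding a dose, and no section says that this moves day 1 of the next cycle. Table 6 gives cycles fixed lengths, abemaciclib is continuous, and day 1 is also the dispensing and diary visit. Subjects may stay on study after stopping either drug (section 3.3), so cycles can be counted without nivolumab. On that reading a hold is a missed infusion and the scan stays where it is. An abemaciclib-only hold need not delay anything, because nivolumab may continue (section 3.1.1). This stands, and it makes the point conditional. It does not remove it: the opposite reading is equally open to a site, and no text settles it.

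Second, the intent looks calendar-based. Sections 7.10.1 and 7.10.5.3 both say 8 weeks, and cycle 3 day 1 is 8 weeks after the first nivolumab dose on day 8 (63 - 7 = 56 days). That is a fair account of where the equivalence came from. But no section names that start date, PFS runs from start of treatment, and neither evaluability limit uses it.

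Third, the consequence is limited. This is a single-arm trial, PFS and DOR are secondary and descriptive, and a subject stays evaluable if any other suitable scan falls inside the limit. All of this stands.

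Two stronger readings are tempting.
- A reader might infer that DOR is lengthened along with PFS. The documents do not support that, because the date of response moves too.
- A reader might take the 12 weeks in section 3.2 as a permitted hold and put the first scan at week 9 + 12 = 21. Those 12 weeks are the duration of a persistent reaction at which nivolumab is permanently discontinued. They are not an allowed hold, so week 21 is an extreme and not an expected size.

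**Conclusion.** The point holds in conditional form. Two things are certain from the text: the cycle rule and the 8-week rule differ by one week at the first scan when counted from cycle 1 day 1, and the two evaluability limits start on different dates. The rest depends on a cycle being delayed and on the site following Table 6.

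Under those assumptions, scan-detected progression is dated late by at most the length of the delay, and PFS lengthens accordingly. The first scan misses the section 7.10.2 limit after more than 21 days of delay on its nominal date, or more than 28 at the early edge. It misses the section 8.4.2 limit after anything from 1 day (baseline scan 21 days old) to 22 days (baseline scan on cycle 1 day 1) on its nominal date. Each case assumes no other scan inside the limit. The frequency of such holds is not given, so the number of subjects affected cannot be estimated.

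A reader might infer that replacement overturns the primary result. At the cut-off, 8/27 has p = 0.098; adding back 1 to 5 excluded non-responders would give 8/28 to 8/32, p = 0.116 to 0.206. Those counts are assumed. The documents give neither how many subjects would be excluded nor whether they would be non-responders, so this shows sensitivity at the cut-off and is not a finding of bias.

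**What to change.** State one calendar rule in Table 6 footnote 11, section 6.2.3, section 7.10.1 and section 7.10.5.3: imaging every 8 weeks from cycle 1 day 1 (+/- 7 days), regardless of dose holds, delayed cycles or discontinuation of either drug, until progression or new anticancer therapy. That end point agrees with section 6.2.6. Remove the cycle numbers as the governing rule.

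Give the 12-week limit in sections 7.10.2 and 8.4.2 the same start date.

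Check: the first scan is then at day 56 (49 to 63). From a 21-day-old baseline scan it is 56 + 21 = 77 days, and 63 + 21 = 84 at the late edge, so it meets both limits as now written, with nothing to spare at that extreme. A calendar rule set at week 9 would not do so: it gives 84 days nominally and 91 at the late edge.

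The cost is wording in four places plus the alignment of two definitions. Subjects without delays need no extra scans, and sample size, type I error and power do not change. The small drawback is that some scans will not coincide with an infusion visit. In an undelayed subject, a scan on cycle 3 day 1 (day 63) is still inside the window. The change concerns assessment timing only and takes no position on how holds should be managed.

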6.1 Screening (Within 28 days of First Dose)

- Signed written and informed consent
- Review and confirm all inclusion/exclusion criteria
- Complete medical history and demographics
- Complete physical examination including but not limited to: height, weight, vital signs (oxygen saturation, heart rate, respiration rate, blood pressure, and oral temperature)
- ECOG performance status
- Concomitant medications
- Clinical laboratory testing including but not limited to:
 - CBC with differential and platelet count
 - Serum chemistries: sodium (Na), potassium (K), chloride (Cl), bicarbonate (HCO₃), blood urea nitrogen (BUN), creatinine (Cr), calcium (Ca), albumin (Alb), total serum bilirubin (TBili), AST (SGOT), ALT (SGPT), alkaline phosphatase (ALP)
 - Prothrombin time (PT)/International normalized ratio (INR)
 - Activated thromboplastin time (aPTT)
 - Thyroid stimulating hormone (TSH)
 - If abnormal, free thyroxine will be performed
- Alpha fetoprotein (AFP)
- HIV serology
 - HIV 1/2 antibody screen; HIV viral load by PCR if antibody screen positive
- Serum pregnancy test for beta HCG (for women of childbearing potential, defined in Appendix A)
- Serologic testing for hepatitis C and hepatitis B:
 - Hepatitis B screening with hepatitis B surface antigen, surface antibody, and core antibody (IgG or total antibody, not IgM); if hepatitis B surface antigen or core antibody is positive, HBV DNA PCR will be performed
 - Hepatitis C screening with HCV antibody; if positive, HCV RNA PCR will be performed. HCV RNA PCR can also be performed on cycle 1 day 1, and results are not required prior to initiating therapy.
 - For subjects known to be positive for hepatitis B or hepatitis C by medical history, viral PCR should be performed concurrently to antibody studies
- Blood draw (50cc) for correlative research studies (procedures described in laboratory manual)
- Per standard of care, baseline imaging including but not limited to chest CT (with or without contrast) and triphasic abdominopelvic CT or MRI, if subject does not have previous documentation within 3 weeks of first dose
- Core or surgical tumor biopsy (procedures described in laboratory manual)

6.2 Study Intervention Phase

All labs and study visits have a window of +/- 4 days. All imaging has a window of +/- 7 days

6.2.1 Cycle 1

6.2.1.1 Day 1 - Baseline Visit

- Focused physical exam
- Vital signs and weight
- ECOG PS
- CBC with differential and platelet count and serum chemistries (Na, K, Cl, HCO₃, BUN, Cr, Ca, Alb, TBili, AST, ALT, ALP)
- AFP (only if elevated at screening)
- Serum pregnancy test for beta HCG (for women of childbearing potential, defined in Appendix A)
- Review of concomitant medications
- HCV and HBV viral PCR if indicated:
 - HBV DNA PCR only if hepatitis B surface antigen or core antibody positive
 - HCV RNA PCR if hepatitis C antibody positive and not performed at screening
- Dispensing of abemaciclib

CONFIDENTIAL

- Baseline AE assessment

6.2.1.2 Day 8

- Focused physical exam
- Vital signs and weight
- ECOG PS
- CBC with differential and platelet count and serum chemistries (Na, K, Cl, HCO₃, BUN, Cr, Ca, Alb, TBili, AST, ALT, ALP)
- Blood draw (50cc) for correlative research studies (procedures described in laboratory manual)
- AE assessment
- Nivolumab treatment

6.2.1.3 Day 15 (biopsy and lab visit when possible on same day between days 15 and 19)

- CBC with differential and platelet count and serum chemistries (Na, K, Cl, HCO₃, BUN, Cr, Ca, Alb, TBili, AST, ALT, ALP)
- Core or surgical tumor biopsy (procedures described in laboratory manual)
- Blood draw (50cc) for correlative research studies (procedures described in laboratory manual)

6.2.1.4 Day 29 (lab visit only)

- CBC with differential and platelet count and serum chemistries (Na, K, Cl, HCO₃, BUN, Cr, Ca, Alb, TBili, AST, ALT, ALP)

6.2.2 Cycle 2

6.2.2.1 Day 1

- Focused physical exam
- Vital signs and weight
- ECOG PS
- CBC with differential and platelet count and serum chemistries (Na, K, Cl, HCO₃, BUN, Cr, Ca, Alb, TBili, AST, ALT, ALP)
- TSH
- PT/INR
- AFP (only if elevated at screening)
- Serum pregnancy test for beta HCG (for women of childbearing potential, defined in Appendix A)
- HBV DNA PCR if hepatitis B surface antigen or core antibody previously positive
- Review of concomitant medications
- Review of abemaciclib pill diary
- Dispensing of abemaciclib and return of unused pills
- AE assessment
- Nivolumab treatment
- Blood draw (50cc) for correlative research studies (procedures described in laboratory manual)

